 □ Interviews, questionnaires, surveys □ Educational or cognitive tests □ Focus groups ☑ Observation ☑ Non-invasive imaging or testing (MRI, EEG, pulse oximetry, etc.) □ Administration of contrast agent □ Imaging procedures or treatment procedures that involve radiation (x-rays, CT scans, CT-guided biopsies, DEXA scans, MUGA or PET scan) □ Biopsy conducted solely for research purposes □ Use of placebo □ Sham surgical procedure □ Collection of data from wearable tech such as Fitbit, Apple Watch, Garmin, motion actigraphs, etc.) 	

☐ Fitness tests or other exertion activities ☐ Use of mobile health apps or other apps

☐ Social media-based research activities☐ None of the above	
7.9 * PROCEDURES / METHODS: (REQUIRED)	
For clinical research, list all study procedures, tests and treatments required for this study, including when and how often they will be performed. If there are no clinical procedures, describe the research activities.	
If some of the activities would occur even if the person were not in the study, as in the case of treatment or tests performed for diagnostic purposes, clearly differentiate between those activities that will be done solely for research purposes and those that are happening as part of routine care.	
Examples may include:	
 additional scans outside standard clinical diagnosis or monitoring additional biopsies to collect tissue for research extra clinic visits extra lab tests not required for clinical care 	
If you have a procedure table, attach it to the submission with your other study documents.	
Patients will be randomized to intra-vaginal culture (IVC) of embryos using INVOcell or traditional in-vitro fertilization (IVF) of embryos. Both groups of patients will receive the same initial workup, consultation and evaluation, ovarian stimulation, cycle monitoring, oocyte retrieval, and embryo transfer. The only difference between the two groups will be the culturing/growth of the embryos, which will be randomized to IVC or IVF. All embryos will be transferred on day 3. The IVC protocol is attached for reference.	
7.10 STANDARD CLINICAL PRACTICE: To what extent, if any, do the planned research proc from the care that people would otherwise receive at this institution or the study site done locally:	

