Based on current research trends, we strongly recommend including the genomic data sharing language in the consent form to allow future sharing, even if you don't anticipate it now. It's easier than trying to reconsent all the specimen donors! 7.13 * TYPE OF SPECIMENS (check all that apply): (REQUIRED) **▼** Blood Tissue (describe below): Existing/archival materials (name source below): --Other (describe below): Describe and/or name source: Because patients will not be randomized to either arm of the study (IVC versus IVF) until the day of trigger, they will receive the standard of care and workup that all infertility patients receive when they come to UCSF Center for Reproductive Health for their care. No additional blood tests, tissue collection or biopsies will be performed beyond the standard of care. Therefore, all patients will have their blood drawn for evaluation of the etiology of their infertility, possible tracking hormone levels during their stimulation cycle, and have embryo transfers performed. 7.14 * SPECIMENS ARE: (check all that apply): (REQUIRED) Leftover specimens from a clinical diagnostic or therapeutic procedure Specimens collected for research purposes only (including extra samples taken during a clinical procedure) ✓ Other Explain **Other**: Specimens collected will be the same that are all part of standard care for patients under infertility evaluation. These include: blood samples and embryos (that will belong to patient and be transferred to uterus or frozen for later use by patient). 7.15 * DESTINATION: Specimens will ultimately be stored (check all that apply): (REQUIRED) Outside Entity: Cooperative group bank □ NIH ☐ Other university Industry sponsor Other UCSF: UCSF repository/bank being established under this protocol Existing UCSF specimen repository/bank with CHR approval Other location at UCSF (please describe) Provide the name of the bank and iRIS approval number (if not being

University of California San Francisco - Center for Reproductive Health - Embryology Lab

the location or lab:

banked at UCSF under this protocol). If you checked 'Other,' please provide

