We expect N=20 to each group (cases and controls, respectively) and given low-stimulation protocols, expect 1-3 embryos per patient. Given these low numbers, summary statistics will be used. For categorical outcomes, frequency tables will be provided. For continuous outcomes, full summary statistics will be provided. This will include mean, standard deviation, minimum, maximum, median and quartiles. To determine the effect of IVC with INVOcell device versus conventional IVF while using oral stimulation or minimal gonadotropins stimulation protocols on: a. Fertilization rate, which is defined by the total number of fertilized oocytes divided by total number of mature oocytes retrieved. This comparison will take place on day-3, as that is when the IVC embryos will be assessed. b. Embryo quality. This is measured by the Gardner grading system. c. Implantation rate, which is defined by number gestational sacs seen on early pregnancy 6-week ultrasound divided by number of embryos transferred. d. Clinical pregnancy rate, which is defined by the number of fetal poles with heartbeat seen on ultrasound divided by the number of embryos transferred. e. Live birth rate, which is defined by the number of living babies delivered divided by the number of transfers. To determine the effect of IVC with INVOcell device versus conventional IVF while using oral stimulation or minimal gonadotropins stimulation protocols on: a. Live birth rate, which is defined by the number of live births divided by the number of transfers		ill be

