summary statistics will be provided. This will include mean, standard deviation, minimum, maximum, median and quartiles. To determine the effect of IVC with INVOcell device versus conventional IVF while using oral stimulation or minimal gonadotropins stimulation protocols on: a. Fertilization rate, which is defined by the total number of fertilized oocytes divided by total number of mature oocytes retrieved. This comparison will take place on day-3, as that is when the IVC embryos will be assessed. b. Embryo quality. This is measured by the Gardner grading system. c. Implantation rate, which is defined by number gestational sacs seen on early pregnancy 6-week ultrasound divided by number of embryos transferred d. Clinical pregnancy rate, which is defined by the number of fetal poles with heartbeat seen on ultrasound divided by the number of embryos transferred e. Live birth rate, which is defined by the number of living babies delivered divided by the number of transfers To determine the effect of IVC with INVOcell device versus conventional IVF while using oral stimulation or minimal gonadotropins stimulation protocols on: a. Live birth rate, which is defined by the number of live births divided by the number of transfers	We expect N=20 to each group (cases and controls, respectively) and given low-stimulation protocols, expect 1-3 embryos per patient. Given these low numbers, summary statistics will be	
a. Fertilization rate, which is defined by the total number of fertilized oocytes divided by total number of mature oocytes retrieved. This comparison will take place on day-3, as that is when the IVC embryos will be assessed. b. Embryo quality. This is measured by the Gardner grading system. c. Implantation rate, which is defined by number gestational sacs seen on early pregnancy 6-week ultrasound divided by number of embryos transferred d. Clinical pregnancy rate, which is defined by the number of fetal poles with heartbeat seen on ultrasound divided by the number of embryos transferred e. Live birth rate, which is defined by the number of living babies delivered divided by the number of transfers To determine the effect of IVC with INVOcell device versus conventional IVF while using oral stimulation or minimal gonadotropins stimulation protocols on: a. Live birth rate, which is defined by the number of live births divided by the number of transfers	summary statistics will be provided. This will include mean, standard deviation, minimum,	

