Randomization risk: You will be assigned to a treatment program by chance, and the treatment you receive may prove to be less effective or to have more side effects than the other study treatment(s) or other available treatments. Side effects risk: You may have side effects while on the study. Everyone taking part in the study will be watched carefully for any side effects. As with anyone undergoing fertility treatments, side effects may be mild or serious. Fertility treatment risks (either Group 1 or Group 2 participants): You will be receiving fertility medications to stimulate your ovaries to grow multiple eggs. Some of the more common side effects from this treatment include: bloating, cramping, nausea, headache, visual changes, hot flashes, and mood changes. You also have a small risk of more serious side effects or complications including ovarian hyperstimulation syndrome (OHSS), dehydration, lightheaded/dizziness, and abdominal discomfort. From the egg retrieval process, there are risk associated with anesthesia and procedural risks such as bleeding, infection and injury that your treatment physician will describe to you in more detail during the consenting process. Your ovaries will be stimulated using the minimal stimulation protocol. This is a lower cost stimulation and sometimes can produce a smaller quantity of eggs than full stimulation. Due to the smaller number of eggs, there may be a reduced pregnancy rate.	
INVOcell device risks (Group 1 participants):	

- There is a small risk that the placement and retention of the INVOcell device may be slightly uncomfortable for the patient, though studies have shown there has been no significant report of discomfort. During the device retention studies performed, 14/15 women reported no or mild discomfort.
- There is also a chance that the device may be expulsed from the vagina. This has never
 occurred with the device, and if it were to occur, you will have been trained on how to
 replace the device into the vagina.
- There is a small risk of failure of embryo development that may occur regardless of which study group you are in. This risk may be slightly increased with the INVOcell device.

Unknown Risks: The experimental treatments may have side effects that no one knows about yet. The researchers will let you know if they learn anything that might make you change your mind about participating in the study.

12.3

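### Multiple pregnancy is never named or counted, and a live birth rate of babies per transfer scores a twin delivery as two successes

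*Combined protocol and SAP*

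**What the plan says.** Embryo numbers. Section 7.25 says the investigators "expect 1-3 embryos per patient" under low stimulation. Section 7.9 says "All embryos will be transferred on day 3". No maximum number to transfer is stated. Section 7.14 describes "embryos (that will belong to patient and be transferred to uterus or frozen for later use by patient", and 7.20 foresees patients returning for stored embryos. The transfer and freezing statements need to be reconciled.

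Outcomes, all in 7.25:
- Primary: "Implantation rate, which is defined by number gestational sacs seen on early pregnancy 6-week ultrasound divided by number of embryos transferred".
- Secondary: "Clinical pregnancy rate, which is defined by the number of fetal poles with heartbeat seen on ultrasound divided by the number of embryos transferred".
- Secondary, first definition: "Live birth rate, which is defined by the number of living babies delivered divided by the number of transfers".
- Secondary, second definition, after a repeat of the lead-in: "Live birth rate, which is defined by the number of live births divided by the number of transfers".

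Risks and monitoring. The fertility-treatment risks in 12.2 are specific: "You also have a small risk of more serious side effects or complications including ovarian hyperstimulation syndrome (OHSS), dehydration, lightheaded/dizziness, and abdominal discomfort", followed by anesthesia, bleeding, infection, injury and a possibly lower pregnancy rate. Multiple pregnancy is not among them. Sections 13.2 and 13.4 set up a committee that meets monthly to look at safety concerns in general terms. Twins or multiples appear nowhere in the available text.

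**The concern.** Multiple pregnancy is the foreseeable consequence of transferring more than one embryo, and the plan has no place where it would be recorded as such. The live birth outcome goes further: under its first definition each additional baby raises the success rate. Two arms with the same number of women delivering would report different live birth rates if one had more twins, and the reader could not tell why.

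The two per-embryo outcomes have a different weakness. Because they count sacs and heartbeats rather than women, the same rate can come from many women with one sac or half as many with two. The hypothesis in 4.1 concerns similarity of clinical pregnancy between the methods. A similar per-embryo rate could therefore hide a difference both in women pregnant and in multiples. The study is a pilot for a possible larger trial, so its definitions may be carried forward.

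**Working it through.** The plan gives no figure for multiple pregnancy and no power calculation, so there is no planned number to reproduce. Arm size is 16 in 9.1 and 9.3 but 20 in 7.25 and 10.6. Both are used below, and the point does not depend on which is right.

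**1. Live birth as babies per transfer.** One transfer per woman; *w* women deliver, *t* of them twins. Women with a live birth = *w*/*n*. Babies per transfer = (*w* + *t*)/*n*. The values of *w* and *t* are illustrative.

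| n | w | t | Women delivering | Babies per transfer |
|---|---|---|---|---|
| 16 | 6 | 0 | 37.5% | 6/16 = 37.5% |
| 16 | 6 | 2 | 37.5% | 8/16 = 50.0% |
| 16 | 6 | 4 | 37.5% | 10/16 = 62.5% |
| 20 | 8 | 0 | 40% | 8/20 = 40% |
| 20 | 8 | 2 | 40% | 10/20 = 50% |
| 20 | 8 | 4 | 40% | 12/20 = 60% |

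Under the second definition a twin delivery may count once. The rate would then stay at 37.5% or 40%.

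**2. The per-embryo outcomes.** If *k* embryos are transferred and each implants with probability *p*, expected sacs are *kp*, and the rate is *kp*/*k* = *p* for any *k*. More embryos per woman does not raise the expected rate. But 16 women with 2 embryos each give 32 embryos, and 10 sacs give 10/32 = 31.3% in either of two cases: 10 women with one sac each (10/16 = 62.5% pregnant) or 5 women with two each (5/16 = 31.3% pregnant, all twins).

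**3. How many multiples to expect.** Inputs: *p* = 31.7% and 33.6%, the implantation rates in 7.6 from the cited non-randomised study of culture to day 3. Independence between embryos is assumed, as is the same *k* for every woman in the arm. P(any sac) = 1 − (1 − *p*)^*k*. P(two or more) = *p*² for *k* = 2, and 3*p*²(1 − *p*) + *p*³ for *k* = 3.

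| k | p | P(any) | P(2 or more) | Share of pregnancies | Women per 16 | Women per 20 |
|---|---|---|---|---|---|---|
| 1 | either | *p* | 0 | 0% | 0 | 0 |
| 2 | 31.7% | 0.534 | 0.100 | 18.8% | 1.6 | 2.0 |
| 2 | 33.6% | 0.559 | 0.113 | 20.2% | 1.8 | 2.3 |
| 3 | 31.7% | 0.681 | 0.238 | 34.9% | 3.8 | 4.8 |
| 3 | 33.6% | 0.707 | 0.263 | 37.2% | 4.2 | 5.3 |

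**4. An illustration from the plan's own background.** For the cited randomised trial, 7.6 gives births per blastocyst of 48.5% (IVC) and 41.7% (IVF), and live birth rates of 55% and 60%. The per-blastocyst percentages fit 16/33 and 15/36. Assume 20 women per arm with one transfer each: 55% and 60% fit 11/20 and 12/20, and doubling every count gives the same rates. Per woman, IVF is ahead, 60% to 55%. Per transfer in babies, IVC is ahead, 16/20 = 80% to 15/20 = 75%. The order reverses because IVC has 16 − 11 = 5 extra babies and IVF 15 − 12 = 3. The arm size is an assumption, so this shows what the definition can do and is not a finding about that trial.

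**The case against.** The strongest reply is that a reader might infer more than the documents support.

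- *All three outcomes reward twins.* They do not. Implantation, the primary outcome, and clinical pregnancy are divided by embryos transferred, so two sacs from two embryos score no higher than one from one. The upward scoring applies only to babies per transfer, a secondary outcome with a second definition that may not share the problem.
- *The plan permits three embryos to be transferred.* It does not say so. One to three is an expected number per patient, offered to explain why only summary statistics are planned. The day-3 sentence can be read as fixing the day, and freezing is foreseen. The number transferred is unstated.
- *The safety board would not see multiples.* This is not shown. Its remit is general and has no closed event list; multiples are neither named nor excluded.
- *Half or more of pregnancies could be multiple.* That needs three embryos and the 44.4-54.5% implantation rates in 7.6. Those are per blastocyst, whereas this trial transfers on day 3.

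It is also fair to say that embryo transfer is meant to be the same in both arms, that 12.2 warns of a lower pregnancy rate with minimal stimulation, that the study is descriptive with no test or margin, and that the consent pages and attached IVC protocol, not available here, may mention multiples.

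All of this stands as a limit on the point. None of it supplies a count of women or of multiples in 7.25, or settles which live birth definition applies.

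**Conclusion.** The point holds in a limited form. Multiple pregnancy is neither named nor counted in the available text. One of two live birth definitions counts a twin delivery as two successes, moving the rate in the example from 37.5% to 50.0% or 62.5% with no change in the number of women delivering. The per-embryo outcomes are not inflated, but they cannot separate twins from two singletons.

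The expected number of multiples per arm of 16-20 is none if one embryo is transferred, about 2 women if two, and about 4-5 if three. This rests on independent implantation, on rates from a non-randomised ICSI study, and on every woman receiving the same number. The real mix is unknown because the plan does not state it. Counts this small support description by arm, not a formal comparison. The documents do not show that either arm would have more multiples.

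**What to change.** - In 7.25, reconcile the two live birth definitions into one: women with at least one live birth, over a stated denominator.
- Report by arm the number of women with two or more gestational sacs, with two or more heartbeats, and with a multiple delivery. Give each over women randomised and over women pregnant, with embryos transferred per woman in the same table as the implantation and live birth rates.
- Name multiple pregnancy in 12.2, and include the count in the monthly review in 13.2 and 13.4.
- Reconcile the transfer statement in 7.9 with the freezing text in 7.14.

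Nothing here proposes how many embryos to transfer. The ultrasound and delivery data are already needed for the planned outcomes, so the cost is one table and a few lines of text. The downside is small counts and one more reported outcome.

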IVC, also called INVO, was developed by Claude Ranoux in 1988 as another method for culturing oocytes or embryos when compared to the conventional laboratory culture method [5]. Since then, the device has been used and studied in multiple countries including: Austria, Bolivia, Brazil, Canada, Ecuador, India, Mexico, Nicaragua, Pakistan, Panama, Spain, Turkey, and Venezuela [5-8]. In addition, INVOcell was FDA approved for use in the United States in November of 2015. There have been numerous studies on the INVO procedure and INVOcell device including evaluation and optimal conditions of the culture such as pH, pCO2 and pO2 [8] to optimal time of intra-vaginal culture [9]. Garcia-Ferreyra et al performed a prospective, non-randomized study that evaluated INVO using intracytoplasmic sperm injection (ICSI) with INVOcell versus conventional ICSI to day 3 and found no significant differences between embryo quality (77% INVO-ICSI versus 86.8% ICSI), pregnancy rate (54.2% INVO-ICSI versus 58.1% ICSI) and implantation rate (31.7% INVO-ICSI versus 33.6% ICSI) [10]. To control for factors between patients, a pilot study performed in 2015, compared sister ocytes (INVO vs IVF) and found similar cleavage rates (93% ± 1.5% IVF versus 97% ± 6% INVO) and a clinical pregnancy rate of 43% per embryo transferred from INVO procedure. In the United States, the device has been FDA approved for IVC for three days, but there is currently research being done to investigate whether IVC for five days (to blastocyst stage) can lead to improved embryo quality and live birth rates. Doody et al performed a randomized controlled trial comparing IVF to IVC that showed no significant differences in the percentage quality of blastocyst transferred when compared to IVF (87.9% IVC, 97.2%, p = 0.09) and live birth rate (55 % IVC, 60 % IVF) [9]. In fact, the implantation and birth rates per blastocyst transferred was actually higher with INVOcell wersus IVF (54.5 versus 44.4% and 48.5 versus 41.7%) [9]. These findings are promising and show that	
7.7 * TREATMENT PROTOCOL: Is this a treatment study, i.e. does this study intend to provid to individuals with a medical or psychological condition: (REQUIRED)	e treatment
⊙ Yes ○ No	
7.8 * COMMON RESEARCH ACTIVITIES: Types of research activities that will be carried out. apply and describe in more detail in the 'Procedures / Methods' section: (REQUIRED)	Check all that

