number of mature oocytes retrieved. This comparison will take place on day-3, as that is when the IVC embryos will be assessed. b. Embryo quality. This is measured by the Gardner grading system. c. Implantation rate, which is defined by number gestational sacs seen on early pregnancy 6-week ultrasound divided by number of embryos transferred d. Clinical pregnancy rate, which is defined by the number of fetal poles with heartbeat seen on ultrasound divided by the number of embryos transferred e. Live birth rate, which is defined by the number of living babies delivered divided by the number of transfers To determine the effect of IVC with INVOcell device versus conventional IVF while using oral stimulation or minimal gonadotropins stimulation protocols on: a. Live birth rate, which is defined by the number of live births divided by the number of transfers 7.26 REFERENCES: List only the 5-10 most relevant references (a separate bibliography can be attached for reference purposes if this study involves novel approaches, agents, or an emerging technology		
 c. Implantation rate, which is defined by number gestational sacs seen on early pregnancy 6-week ultrasound divided by number of embryos transferred d. Clinical pregnancy rate, which is defined by the number of fetal poles with heartbeat seen on ultrasound divided by the number of embryos transferred e. Live birth rate, which is defined by the number of living babies delivered divided by the number of transfers To determine the effect of IVC with INVOcell device versus conventional IVF while using oral stimulation or minimal gonadotropins stimulation protocols on: a. Live birth rate, which is defined by the number of live births divided by the number of transfers 7.26 REFERENCES: List only the 5-10 most relevant references (a separate bibliography can be attached for reference purposes if this study involves novel approaches, agents, or an emerging technology 	number of mature oocytes retrieved. This comparison will take place on day-3, as that is	

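### Section 7.25(b) gives embryo quality no denominator, so by default it covers only embryos gradable on day 3, a base that can differ between arms after randomisation

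*Combined protocol and SAP*

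**What the plan says.** The whole definition of the outcome in section 7.25 is "b. Embryo quality. This is measured by the Gardner grading system". The general rule there is that "For categorical outcomes, frequency tables will be provided". Nothing states the base of the table, the unit of analysis, which grades count as good, or how an arrested, degenerate or lost embryo is entered.

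The other outcomes in 7.25 do have a base. The fertilization rate is "defined by the total number of fertilized oocytes divided by total number of mature oocytes retrieved", and the plan adds: "This comparison will take place on day-3, as that is when the IVC embryos will be assessed". Implantation and clinical pregnancy are per embryo transferred, and live birth is per transfer. No outcome is per woman randomised.

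Three other places matter. Section 7.9 says "All embryos will be transferred on day 3". Section 7.13 places randomisation on the day of trigger, before retrieval. Section 12.2 says "There is a small risk of failure of embryo development that may occur regardless of which" study group the woman is in, and continues: "This risk may be slightly increased with the INVOcell device".

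**The concern.** A table of grades needs embryos to grade. IVC embryos are assessed on day 3 and transfers take place on day 3, so the natural base is the embryos present that day. That set is formed after randomisation, and the plan itself expects that the event shaping it may be somewhat more common in one arm. A percentage taken over such a set no longer compares the randomised groups. If the embryos that drop out are mainly poor, the percentage of good ones rises although the device has produced no extra good embryo. A woman with no embryo on day 3 does not appear in the table at all.

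At stake is what the pilot passes on to the larger trial mentioned in 7.25: a quality estimate that can improve because embryos were lost.

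**Working it through.** The plan states no expected quality rate, power or sample-size calculation for this outcome, so there is no figure to reproduce. The check shows how the default table behaves.

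**Inputs**
- *g*, the share of good embryos before any extra loss: 77% and 86.8%. These are the two figures in section 7.6, used only as a plausible range.
- *L*, the extra fraction of embryos lost in the IVC arm, and *f*, the part of that loss that is poor: assumptions, because no rate is given.
- Embryos per woman: 1 to 3 (section 7.25). Women per arm: 20 (7.25, 10.6) or 16 (9.1, 9.3).

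**Step 1. Shift in the reported share.** Reported IVC share = (g − L(1 − f)) / (1 − L).

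| Assumed extra loss | g = 77% | g = 86.8% | Fall in good embryos |
|---|---|---|---|
| 10%, all poor | 0.77/0.90 = 85.6% (+8.6) | 0.868/0.90 = 96.4% (+9.6) | none |
| 15%, two thirds poor | 0.72/0.85 = 84.7% (+7.7) | 0.818/0.85 = 96.2% (+9.4) | 0.05/0.77 = 6.5%; 0.05/0.868 = 5.8% |
| 5%, all poor | 0.77/0.95 = 81.1% (+4.1) | 0.868/0.95 = 91.4% (+4.6) | none |
| 2%, all poor | 0.77/0.98 = 78.6% (+1.6) | 0.868/0.98 = 88.6% (+1.8) | none |

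**Step 2. How strong the first two rows are.** Each removes poor embryos equal to 10% of all embryos. That is 0.10/0.23 = 43% of the poor ones at g = 77%, and 0.10/0.132 = 76% at g = 86.8%.

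**Step 3. When the share and the yield part company.** Let LG and LW be the extra fractions of good and weak embryos lost. Share = g(1 − LG) / [g(1 − LG) + (1 − g)(1 − LW)]. Good embryos per woman = n·g·(1 − LG). With n = 2 and g = 0.77, and no extra loss in the control arm (share 77.0%, 1.54 good embryos per woman):
- LG = 0, LW = 0.5: share 0.77/0.885 = 87.0%, yield 1.54 (unchanged).
- LG = 0.2, LW = 0.5: share 0.616/0.731 = 84.3%, yield 1.23.
- LG = LW = 0.2: share 0.616/0.800 = 77.0%, yield 1.23.
- LG = 0.5, LW = 0.2: share 0.385/0.569 = 67.7%, yield 0.77.

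So an equal or higher share with a lower yield requires LG > 0 and LW ≥ LG.

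**Step 4. Effect of a fixed base.** If failed embryos stay in the denominator as not good, the share becomes g(1 − LG). The second case in step 3 then reads 61.6% against 77.0%, in line with the fall in yield.

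**Step 5. Scale.** Each arm would have between 16 × 1 = 16 and 20 × 3 = 60 embryos. At a share near 80%, the 95% half-width for a difference is 1.96·√(2 × 0.16/60) = 14 points at best and 1.96·√(2 × 0.16/16) = 28 points at worst, before allowing for embryos from the same woman.

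**The case against.** The strongest reply is that the plan is silent rather than wrong. A reader might infer that 7.25 restricts grading to embryos alive on day 3. No sentence says so, and the attached IVC protocol, which might settle it, is not among the documents. This stands: the restriction is the likely default, not a stated rule.

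A reader might also infer that losing weak embryos leaves a woman with fewer good ones. It does not. In step 3 the yield is unchanged when LG = 0, and it falls only when good embryos are lost as well.

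Section 7.6 does not show the artefact at work. It reports "embryo quality (77% INVO-ICSI versus 86.8% ICSI") without saying over which embryos, and the device arm is the lower one. The blastocyst figures there (87.9% against 97.2%) point the same way, and the sister-oocyte pilot gives cleavage rates of 97% with the device and 93% without.

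The 10-15% losses are large for a risk that section 12.2 calls small and perhaps slightly raised, and the resulting shifts lie within the sampling noise of step 5. The day-3 fertilization rate per mature oocyte may also reveal part of the loss. But an oocyte that fertilised and then arrested can still count as a success there, so it does not measure the yield of good embryos.

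All of this limits the size of the problem. It does not supply the missing denominator or any summary that follows the randomised groups.

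**Conclusion.** The point holds as a gap in definition with a predictable direction of bias. With no denominator stated, the grade table will by default describe a set selected after randomisation, and the plan itself names a reason why selection may differ by arm. When weak embryos are lost at least as often as good ones, the table can show IVC as equal or better; good embryos per woman then fall only if some good ones are also lost.

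The size cannot be determined from the documents. Shifts of about 8 to 10 points (7.7 to 9.6) need assumed extra losses of 10-15%, mostly poor embryos; an extra 2%, all poor, gives 1.6 to 1.8 points. The documents do not support a claim that the device flatters quality, nor that it lowers yield.

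The outcome is secondary and descriptive, so no error rate, test or sample size is affected. The change is worth making because the pilot is meant to inform a larger trial.

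**What to change.** In section 7.25(b):
- Add the number of good-quality day-3 embryos per woman randomised, set to zero when she has none.
- Add good-quality day-3 embryos per mature oocyte retrieved, the denominator already used in 7.25(a).
- Count arrested, degenerate or lost embryos as not good.
- State in advance which grades count as good.
- Keep the grade table as descriptive, labelled 'among embryos present on day 3'.

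The cost is small. Mature oocyte counts and grades are needed anyway for 7.25(a) and (b). The documents do not list the data items, so it should be confirmed that failed embryos are recorded. One cut-off must be chosen. The per-woman yield also reflects oocyte number and fertilization, so it answers a broader question than the grades do. It should therefore stand beside the table and not replace it.
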